#### 2 SPECIFIC AIMS / HYPOTHESIS

## 2.1 Primary Objectives

1. Evaluate the safety of the RestoreX® device when used 30 minutes once daily, twice daily, three times daily, and in an open label fashion

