#### 3.1 Limitations with Current PTT Devices

Currently available PTT devices have several notable limitations:

• The first and most important limitation is regarding regulatory approval. As a general class, orthotic-type devices intended to correct a deformity are considered Class I devices by the FDA. However, current devices are not designed to correct penile curvature, but are predominantly designed to lengthen the penis. As such, they fall outside of the Class I category and are therefore considered as novelty items with no claims as to role or efficacy. Only one PTT device (Andropenis®) has retroactively registered with the FDA as a 510k exempt Class II device (pending review by the FDA).

- A second limitation is that the devices are very difficult to use and often result in mild, temporary patient pain and discomfort. The clamping portion of the device alone often results in pinching of skin and transient pain with device application. In the largest (n=96) randomized controlled trial (RCT) performed of the device in men with PD, the authors noted penile erythema occurring in 2% and transient pain in 25%.[17]
- A third limitation is the duration of use required. Currently, the Andropenis® device is recommended to be used for 9 hours daily over a period of at least 3 months. This duration of use is clinically very challenging to achieve, and in our practice we have found that most patients are not able to utilize the device for over 1-2 hours daily.
- The Andropenis® device achieves very minimal traction on the penis. In assessments of patients utilizing the device, often no traction is achieved.
- Existing PTT devices do not have a mechanism by which curvature can be corrected. They are restricted to lengthening alone. They also are not allowed to make any claims specifically on lengthening in the US.
- With the exception of one device, existing PTT systems have not undergone clinical testing.

Given these numerous limitations, a novel PTT device has been developed at Mayo Clinic (Figure 1). The primary objective of the device was to assist in the treatment of PD, either as a primary or adjunctive therapy. The device addresses each of the above bullet points, and is designed to be a minimally-invasive alternative to existing treatments.

Figure 1 – RestoreX® device

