#### 4.1.5 Consent and Enrollment

Following initial recruitment, patients will be scheduled for an introductory and orientation appointment. Specific study details and requirements will be reviewed at that time, and if the patients express interest in participating, a formal consent will be reviewed.

If the patient successfully completes the consenting process, they will undergo initial assessments as described later in the protocol. At enrollment, all patients will be assigned a study identifier, with a master list maintained in a password protected database (Mayo server) linking the patient to the identifier. A goal of 25 patients will be enrolled into each arm of the study, with an estimated 120 enrolled to achieve this number (due to anticipated dropouts, failure to comply). It is estimated that 250 patients will need to be screened to enroll the 120 patients.

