## 4.2 Study Schema

Once patients have agreed to receive further information on the study, an initial consult will be established. Patients who are currently taking other therapies for PD will be requested to stop these therapies for a minimum of 4 weeks prior to the appointment to assure an adequate washout period prior to being enrolled.

During the initial appointment, the patient will receive a description of the study, initial education on how to use the device properly, and informed consent. Those consenting to the procedure will

receive initial study assessments (see below). Those wishing additional time to consider enrollment may be rescheduled to a later date if desired. Once consent is completed, the patients will be randomized into one of four groups: PTT 30 min 1x/day, 30 min 2x/day, 30 min 3x/day, or control (no treatment).

Patients will then begin using the devices as previously instructed for the times appropriate to their group. After 3 months (+1.5 months permitted), patients will return for subsequent assessments (see below). After completion of the subsequent assessments, patients will begin a 3-month, open-label phase of the trial. During this period, the patients will be allowed to use the device for 30 minutes at a time, with a frequency to be determined by the patient.

After completion of the open-phase portion of the trial, patients will undergo final assessments, which are identical to the 3-month assessments. Patients will then be encouraged to self-report any additional adverse events (AE's) that they encounter over the subsequent 3 months after discontinuing the therapy and will be contacted by telephone for a final question / adverse event assessment (9 months after study initiation).

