#### 4.2.3 Randomization and Blinding Protocol

Following enrollment and completion of the initial curvature assessment, patients will be categorized into one of six strata based on baseline variables (curvature 30-60 degrees, >60 degrees by dorsal primary, lateral primary, and ventral primary). Each strata will have a separate randomization table provided such that one of four possible outcomes will occur no less frequently than every four cases. This is done to better account for baseline variables that may impact outcomes and to assist with matching groupings appropriately.

The explanation of which grouping the patient is assigned will then be reviewed, and the patient will be provided with a RestoreX® device (if applicable).

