#### 4.3.3 Statistical Analysis

All data will be entered into JMP Pro 10.0.0 (SAS Institute, Cary, NC). Differences between groupings will be analyzed using tests appropriate to the specific conditions: Wilcoxon, matchedpairs, student's t-test, ANOVA, ANCOVA, chi-squared, or Fisher's tests. All relevant tests will be 2-sided, with a p-value of <0.05 defined as significant. Differences in AE's will be determined based on total number of reported events as well as individual assessments of each individual event.

During the first phase of the study, results will be analyzed as a whole to determine the percentage of men who were non-compliant (both in methods of utilizing the device and percentage of time spent using the device) or dropped out. These data will determine the ability of men to utilize the device as recommended. Data will be analyzed both with and without these non-compliant / dropout men included. Non-compliance will be determined by failure to bury the white indicator line regularly with straight stretch, failure to achieve 90 degree bending during majority of uses, and failure to perform traction for at least 90% of days recommended.

Analyses will be performed using comparisons within patients (changes from baseline to 3 months, from 3 months to 6 months, from baseline to 6 months) and between groupings. ANCOVA will be used (adjusting for baseline values of curvature direction, curvature degree, and baseline penile length). Additional analyses will be performed to analyze the impact of prior treatments (such as intralesional injections) on outcomes. The use of ANCOVA is anticipated to increase the effect size slightly to 0.302 (assuming R^2 value of 0.2 for curvature direction, curvature degree, and baseline penile length).

Assessments will also be performed comparing any degree of traction (i.e. groups 2-4) against no traction. Additional assessment will also be performed based on the total duration of traction applied (time per day multiplied by number of days used) to assess for differences in outcome variables.

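### Non-compliance and dropout in the first phase are summarised as one pooled percentage, which cannot show whether men can keep to each of the three daily schedules

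*Combined protocol and SAP*

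**What the plan says.** Section 4.3.3 gives one specific instruction for adherence. In the first phase "results will be analyzed as a whole to determine the percentage of men who were non-compliant", in technique or in share of time used, or who dropped out. It then gives the purpose: "These data will determine the ability of men to utilize the device as recommended".

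Three criteria define non-compliance. Two concern technique: burying the indicator line on straight stretch, and reaching 90 degrees of bend in most uses. The third is "failure to perform traction for at least 90% of days recommended". Outcome data are then to be analysed both with and without non-compliant men and dropouts.

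Section 4.2 randomises men to four groups: "PTT 30 min 1x/day, 30 min 2x/day, 30 min 3x/day, or control (no treatment"). Section 4.2.3 hands over a device at assignment only where one applies. Section 4.1.4 says participants would receive a device free of charge, but controls are untreated during the randomised three months. I take those three months to be the first phase.

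The primary objective in section 2.1 is written by schedule: "Evaluate the safety of the RestoreX® device when used 30 minutes once daily, twice daily, three times daily", and in open-label use.

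**The concern.** The percentage is meant to show whether men can do what they were told to do, and they were told different things by arm. A figure pooled over 30, 60 and 90 minutes a day describes none of the schedules tested. Randomisation would allow a fair comparison of adherence between schedules, but the only instruction specific to this measure does not ask for one.

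Two further gaps affect the same figure. First, no denominator is given. All three criteria presuppose a device, so controls cannot be rated on them, although controls can drop out. Second, the time criterion counts days, not sessions or minutes, so it can miss skipped second or third sessions.

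The safety comparison by schedule is harder to read without knowing how far each arm followed its schedule. The analyses with and without non-compliant men have a similar difficulty: controls can be removed only for dropout, so exclusions may fall unevenly across arms, and a pooled percentage would not show it.

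**Working it through.** **Inputs.** Arm sizes come from section 4.1.5: "A goal of 25 patients will be enrolled into each arm of the study, with an estimated 120 enrolled to achieve this number". That is 4 × 25 = 100 men as the goal and 120/4 = 30 per arm at enrolment. The implied overall loss is 1 − 100/120 = 16.7%. No non-compliance rate is stated, overall or by arm, so there is none to reproduce and every rate below is an assumption. The plan's detectable ANOVA effect for four arms of 25 does reproduce (0.33699 against the stated 0.3370), but nothing here depends on it.

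**Pooling, 30 men per arm.** The device-arm pooled rate is the total non-compliant divided by 90.

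| Assumed rates (1x / 2x / 3x daily) | Non-compliant men | Pooled |
|---|---|---|
| 10% / 30% / 50% | 3 + 9 + 15 = 27 | 27/90 = 30% |
| 30% / 30% / 30% | 9 + 9 + 9 = 27 | 27/90 = 30% |

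The two patterns give the same figure, with the same exact 95% interval of 20.8% to 40.6%.

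**Denominator, same 27 men.**
- Device arms only: 27/90 = 30%.
- Controls included and coded compliant: 27/120 = 22.5%. The ratio is 90/120 = 0.75.
- Controls included and coded as not using the device: (27 + 30)/120 = 47.5%.

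The factor 0.75 needs equal arms and controls coded compliant. Six strata with separate randomisation tables need not give exactly equal arms. The factor does not carry over to dropout.

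**By-arm precision (exact 95% intervals).**
- 3/30: 2.1% to 26.5%
- 9/30: 14.7% to 49.4%
- 15/30: 31.3% to 68.7%
- For reference, 5/25: 6.8% to 40.7%; 6/30: 7.7% to 38.6%

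These are wide, but a steep gradient would still be visible. For 3, 9 and 15 of 30, the expected counts are 9 non-compliant and 21 compliant per arm. Chi-squared = (36 + 0 + 36)/9 + (36 + 0 + 36)/21 = 8.00 + 3.43 = 11.43 on 2 df, and p = exp(−11.43/2) ≈ 0.003.

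**The day-based criterion.** A man assigned three sessions who does one session every day meets 100% of days but only 30/90 = 33% of the recommended time. With two sessions assigned, the corresponding share is 30/60 = 50%. Both pass the day criterion.

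**The case against.** Section 4.3.3 opens by saying that differences between groupings will be tested, and lists chi-squared and Fisher's tests. Non-compliance is categorical, so a by-arm comparison is allowed. The planned analysis of total traction time needs individual use data, so arm-level data should exist. A reader might infer that the plan discards the by-arm information; the text does not say that. What stands against the objection is that permission is not commitment. The one sentence written for this measure asks for a pooled figure, and the total-time analysis concerns outcomes.

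Two of the three criteria are technique items that are the same in every device arm, and the third applies the same 90% threshold to days. A pooled technique figure is therefore a reasonable summary, and it can stay as a secondary one. It still cannot show whether technique or days used worsen as the schedule lengthens.

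The natural reading is that controls are not rated at all. That is fair: the documents do not show that controls will dilute the figure, only that the denominator is not stated.

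A reader might also take the remark in section 3.1 that "most patients are not able to utilize the device for over 1-2 hours daily" as evidence that the 90-minute arm will fail. It does not support that. The remark concerns another traction device, recommended for 9 hours daily, and the new device is described as designed to address such limitations. It shows only that the protocol regards wear time as a practical constraint.

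Finally, adherence is not a listed objective in sections 2.1 or 2.2. That is correct, and it limits the weight of the point.

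**Conclusion.** The point holds as an improvement to a supporting measure. Followed as written, section 4.3.3 yields one percentage that cannot tell a strong schedule effect on adherence from none, and no other section commits to non-compliance or dropout by arm. The size cannot be stated from the documents, because they give no rate; the 10/30/50% pattern is an assumption chosen to show the mechanism. The effect of including controls is conditional on how they are coded: three quarters of the device-arm non-compliance rate if compliant, a higher figure if coded the other way, and no effect if they are left out.

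No stated number is wrong. It would go too far to conclude that the primary safety objective is undermined, or that any schedule is likely to prove unworkable.

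**What to change.** In section 4.3.3, replace 'as a whole' with 'by randomised arm', and specify:

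- Report non-compliance and each of its three components for the three device arms, with all men randomised to that arm as denominator and an exact 95% CI. State how men who drop out before adherence can be rated are counted.
- Leave controls out of the non-compliance figure.
- Report dropout separately for all four arms.
- Compare arms with the Fisher's or chi-squared tests already listed.
- Report by arm the percentage of recommended time used, which the section already mentions, so that missed second or third sessions are visible.
- Keep a pooled device-arm figure as a secondary summary.

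This is a wording change. It needs no extra men or visits, and the total-time analysis already requires individual use data. The downside is wide by-arm intervals at 25 to 30 men per arm, so the results should be read as estimates with intervals. A non-significant test should not be taken as evidence that adherence is equal across schedules.

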## 2.2 Secondary Objectives

- 1. Compare changes in stretched penile length following completion of 3 months of RestoreX® therapy as well as following an open-label period within and among treatment groups.
- 2. Compare changes in penile curvature following completion of 3 months of RestoreX® therapy as well as following an open label period within and among treatment groups
- 3. Compare outcomes of subjective questionnaires assessing erectile function, PD diseasespecific domains, satisfaction, ability to achieve sexual intercourse, and pain among treatment groups
- 4. Compare satisfaction with the RestoreX® device to alternative forms of PTT among treatment groups
- 5. Compare satisfaction with the RestoreX® device to alternative PD therapies among treatment groups

The current study hypothesis is that deformities relating to PD (penile length loss, curvature) can be treated with penile traction therapy.

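### The one named ANCOVA covariate set leaves out the baseline IIEF-15 and PDQ scores, so questionnaire comparisons between arms may be less precise than the collected data allow

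*Combined protocol and SAP*

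**What the plan says.** Secondary objective 3 (section 2.2) reads: "Compare outcomes of subjective questionnaires assessing erectile function, PD diseasespecific domains, satisfaction, ability to achieve sexual intercourse, and pain among treatment groups". Sections 4.2.1 and 4.2.2 schedule the IIEF-15 and PDQ before randomisation and at 3 and 6 months (the PDQ is printed as PDO in 4.2.1, taken here as a text-reading slip).

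Section 4.3.3 gives three pieces of guidance on analysis, and none is tied to the questionnaires:

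- a general list for between-group differences: "tests appropriate to the specific conditions: Wilcoxon, matchedpairs, student's t-test, ANOVA, ANCOVA", followed by tests for categorical data;
- the time structure: "comparisons within patients (changes from baseline to 3 months, from 3 months to 6 months, from baseline to 6 months) and between groupings";
- one ANCOVA specification: "ANCOVA will be used (adjusting for baseline values of curvature direction, curvature degree, and baseline penile length", with its expected gain worked out "assuming R^2 value of 0.2 for curvature direction, curvature degree, and baseline penile length".

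On size, section 4.1.5 says: "A goal of 25 patients will be enrolled into each arm of the study". The power statements in 4.3.2 concern curvature and, in words only, length. No power statement covers a questionnaire.

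**The concern.** The covariate set suits the anatomical outcomes. A curvature model adjusts for baseline curvature, and a length model for baseline length. Applied to an IIEF-15 or PDQ score, the same set adjusts for anatomy and omits that score's own baseline, which is usually the strongest single predictor of a follow-up score.

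Three readings of the plan are open for the questionnaires:

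1. The named set applies, so scores are adjusted for anatomy only.
2. Change or follow-up scores are compared without covariates.
3. Own-baseline ANCOVA is chosen from the general list.

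Only the third makes full use of the baseline scores. Under the other two, objective 3 is generally estimated with wider intervals than the data allow, in a trial of about 25 men per arm. Stratification (4.2.3) uses curvature degree and direction, so it does not directly balance questionnaire scores. Naming the model in advance also removes an analysis choice that could otherwise be made after the data are seen.

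**Working it through.** **The plan's own figures.** Inputs are four arms of 25 (N = 100), two-sided alpha 0.05 and 80% power, from 4.3.2 and 4.3.3. Solving the noncentral F (3 and 96 df, noncentrality N f²) gives f = 0.33699, against 0.3370 stated. With noncentrality N f²/(1 − R²), R² = 0.2 and 0 to 5 covariate degrees of freedom, f = 0.3014 to 0.3018, against 0.302 stated. Both reproduce, and neither concerns a questionnaire.

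**Assumed inputs.** The documents give neither r (baseline to follow-up correlation of a score) nor k (baseline SD divided by follow-up SD). I take r = 0.3, 0.5, 0.7 and k = 0.8, 1.0, 1.2.

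**Formulas**, in units of the follow-up variance:

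- follow-up score alone: 1
- change score: k² + 1 − 2rk
- own-baseline ANCOVA: 1 − r²
- change minus ANCOVA: (k − r)², never negative
- cost of estimating one slope: 1 + 1/(100 − 4 − 2) = 1.0106

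Example at r = 0.5, k = 1.0: the change-score variance is 1 + 1 − 1 = 1.00 and the ANCOVA variance is 0.75. The net ratio is 0.75 × 1.0106 / 1.00 = 0.758, a 24% cut. A change-score analysis would need 25/0.758 = 33.0 men per arm to match it.

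**Against a change score**

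| k | r | Var(change) | Var(ANCOVA) | Cut before cost | Net ratio | Net cut | Equivalent n per arm |
|---|---|---|---|---|---|---|---|
| 0.8 | 0.3 | 1.16 | 0.91 | 22% | 0.793 | 21% | 31.5 |
| 0.8 | 0.5 | 0.84 | 0.75 | 11% | 0.902 | 10% | 27.7 |
| 0.8 | 0.7 | 0.52 | 0.51 | 2% | 0.991 | 1% | 25.2 |
| 1.0 | 0.3 | 1.40 | 0.91 | 35% | 0.657 | 34% | 38.1 |
| 1.0 | 0.5 | 1.00 | 0.75 | 25% | 0.758 | 24% | 33.0 |
| 1.0 | 0.7 | 0.60 | 0.51 | 15% | 0.859 | 14% | 29.1 |
| 1.2 | 0.3 | 1.72 | 0.91 | 47% | 0.535 | 47% | 46.8 |
| 1.2 | 0.5 | 1.24 | 0.75 | 40% | 0.611 | 39% | 40.9 |
| 1.2 | 0.7 | 0.76 | 0.51 | 33% | 0.678 | 32% | 36.9 |

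Simulating 20,000 trials of 4 × 25 with no treatment effect gave net ratios within 0.003 of these. The estimated differences averaged about zero under both methods, so bias is not at issue.

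**Against an unadjusted follow-up score**, at any k, the net cuts are 8%, 24% and 48% at r = 0.3, 0.5, 0.7. This comparator matters only if the planned changes from baseline are not used between arms.

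**Interval width.** The 95% half-width for a difference between two arms is t × √(2/25 × variance), with pooled four-arm error and t = 1.985. In follow-up SDs, at r = 0.3, 0.5, 0.7:

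- own-baseline ANCOVA (95 df, including the 1.0106 factor): 0.54, 0.49, 0.40
- change score, k = 0.8: 0.60, 0.51, 0.40
- change score, k = 1.0: 0.66, 0.56, 0.43
- change score, k = 1.2: 0.74, 0.63, 0.49
- follow-up score alone: 0.56 at any r

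**When ANCOVA loses.** A change score is more precise only if (k − r)² < (1 − r²)/94. That means k between 0.41 and 0.59 at r = 0.5, or between 0.63 and 0.77 at r = 0.7. The loss is then at most about 1%.

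**Reading 1.** With the anatomical covariates in both models, the same formulas hold if r is read as the partial correlation and k as the ratio of residual SDs after those covariates. For the detectable effect, suppose anatomy explains 0 to 20% of questionnaire variance (assumed). The detectable f with anatomy alone is then 0.337 to 0.302. Adding the own baseline at a partial r of 0.5 lowers it to 0.292 to 0.261.

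**The case against.** The strongest reply is that the plan contains no error here. ANCOVA is on the list of permitted tests. The named set sits beside a power calculation for curvature, so it was probably written for curvature and length, where it already includes the own baseline. Changes from baseline are also planned, so the questionnaire baselines would not be wasted. The size of the gain rests on values of r and k that the documents do not give, and the largest gains need k = 1.2. If the entry criteria narrow the baseline scores, k would fall below 1, where the gains shown are smallest. Some items under objective 3 may be ordinal or have no baseline, and the attached forms are not available to settle this.

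Much of this stands. The point concerns efficiency and pre-specification on one secondary objective, the realistic comparator is a change score, and the gain can be negligible. It does not remove the point. A change score still carries an excess variance of (k − r)², and nothing in the plan directs the analyst to own-baseline ANCOVA. If the set was meant only for curvature and length, the questionnaire model is left unstated.

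On cost, one degree of freedom is right where the anatomical covariates are already in the model. Moving from no covariates to all five degrees of freedom (direction 2, degree 1, length 1, own baseline 1) would inflate variance by 5/(100 − 4 − 5 − 1) = 5.6%, before crediting the variance they explain.

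**Conclusion.** The concern holds as a modest, low-cost improvement. Section 4.3.3 permits own-baseline ANCOVA for the IIEF-15 and PDQ but does not specify it, and its only stated covariate set lacks those baselines. Against a change score, the net cut in error variance runs from 1% to 47% over the assumed ranges of r and k, equivalent to about 25 to 47 men per arm. No single figure within that range can be defended from the documents. The result applies to continuous scores with a pre-randomisation value. Whether pain is among them depends on forms that are not available. Because allocation is randomised, validity is not affected.

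**What to change.** Add to section 4.3.3 that between-arm comparisons of continuous questionnaire scores measured at baseline (IIEF-15 and PDQ domains, and pain if a baseline score exists) use ANCOVA with that score's own pre-randomisation value, in addition to any anatomical covariates. Keep rank-based tests for ordinal or heavily skewed items, and exclude outcomes with no baseline, such as device satisfaction.

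In the same sentence it is worth naming the 3-month comparison as the contrast of the randomised schedules. Afterwards "patients will begin a 3-month, open-label phase of the trial", and use then continues "with a frequency to be determined by the patient". This is a side point, and the covariate change does not depend on it.

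The cost is one or two sentences of protocol text and one degree of freedom per model, about 1% variance inflation at 4 × 25. No new data are needed, and the stated power figures stay as they are.

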PTT for the treatment of PD has been the subject of several studies.[14] While current evidence for PTT as monotherapy for PD is limited by small cohort sizes and low quality methodology, several studies have suggested significant improvements in stretched penile length (SPL), penile curvature (in acute phase of PD), and/or patient satisfaction.[15-17] PTT in conjunction with intralesional injections including verapamil and interferon has been assessed as well, with significant improvements found in SPL and no significant differences identified on penile curvature.[18-20]

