## 3.3 Significance

The development of a novel PTT which addresses the above limitations is a significant milestone. As previously noted, no PTTs are currently designed to correct PD curvature, and only limited data are available on PTT use in this manner. In the absence of a more conservative therapy, the most common current first line treatment for PD is collagenase clostridium histolyticum (Xiaflex®). This therapy requires 10 physician visits over a 5 month period and costs >\$50,000 for a full treatment series. It also results in notable adverse events including risk of penile fracture and significant penile ecchymoses. The only other viable alternative is surgical management. This is associated with multiple undesirable adverse effects including penile shortening, penile edema, loss of penile sensation, and recurrence of curvature over time.

Traction therapy has been used in many applications including limb and dental orthotics (braces) with success for many years. It however has not been successfully applied in the case of chronic PD, as this has previously not been an area of legitimate scientific research and treatment. If the current study demonstrates the safety and efficacy of the current therapy on improving penile curvature, it has the possibility of displacing other treatments as a first line option for the treatment of PD. This would not only be very cost-effective (for patients and the overall healthcare system), it would also provide a less-invasive option for treatment with fewer long-term risks. It therefore has the possibility of changing the entire paradigm for managing the condition of PD.

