#### 4.2.1 Initial Study Assessments

- Obtained prior to randomization
- Objective assessments to be obtained by providers blinded to study arm
  - o Penile length measured from pubic symphysis to glanular corona and penile tip
  - Penile curvature
    - Measured in A/P and lateral planes using a goniometer (per standard protocol)
    - Direction of curvature also assessed
    - Curvature document as uniplanar (i.e. 60 degrees dorsal, 30 degrees lateral) and composite (i.e. 90 degrees composite)
  - o Distance to curve measured from concave portion of curvature to corona of glans
  - o Indentations / hourglass deformities noted
  - Where possible (patients may decline), photographs obtained of the penis in the lateral and dorsal curvature after a pharmacologic erection has been obtained (per routine curvature assessment protocol). Images will be de-identified.
- Questionnaire on prior relevant disease history
- Subjective questionnaires
  - o IIEF-15
  - o PDO
  - Additional questions pre-treatment

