## 4.3.2 Power Analysis

This is the first study which will be performed for this specific device. As such, the objectives are to assess safety with various dosing protocols. Regarding our secondary end points of penile length and curvature improvement, prior studies evaluating the role of PTT in the early phase of PD have

demonstrated significant improvements with study sizes of 96 patients, which is consistent with the current study schema.[17]

A power analysis was also performed using ANOVA with anticipated sizing of 25 individuals into 4 arms. This provides an effect level of 0.3370 using 80% power, with 0.05 significance established for curvature assessment. Therefore, the study is likely powered to demonstrate large changes in curvature but may not be adequately powered to identify small or medium differences in curvature between groupings. The study is adequately powered to detect reasonable changes in penile length.

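### Disease duration or phase is not used in the curvature analysis, although the cited evidence of curvature benefit comes from acute disease: a cheap improvement

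*Combined protocol and SAP*

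**What the plan says.** The adjusted analysis in section 4.3.3 is an ANCOVA "adjusting for baseline values of curvature direction, curvature degree, and baseline penile length". The other analyses named there concern prior treatments, any traction against none, and total traction time. The six randomization strata (section 4.2.3) cross two bands of curvature degree with three directions. Eligibility (sections 4.1.1 and 4.1.2) admits adult men already diagnosed with Peyronie's disease and sets no limit on phase or duration.

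Three places bear on phase:

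- Section 3 lists outcomes that improved in earlier traction studies. Only curvature carries a phase qualifier: "penile curvature (in acute phase of PD".
- Section 3.3 says of traction: "It however has not been successfully applied in the case of chronic PD". The sentence goes on to give the reason, which is that this had not been a field of legitimate research.
- Section 4.3.2 supports the study size by citing 96-patient work in early disease.

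Section 4.2.1 lists among the assessments made before randomization a "Questionnaire on prior relevant disease history". The form itself is not in the documents.

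**The concern.** The protocol draws its evidence on curvature, and part of its case for the sample size, from early disease. It then enrols men at any stage and plans nothing that uses stage. If duration or phase predicts curvature change beyond the covariates already chosen, leaving it out gives away precision in a trial that concedes limited power for small or medium curvature differences. With 25 men per arm, the arms may also differ noticeably in phase by chance, and an adjustment added after seeing such a difference would be open to challenge. Finally, readers of a curvature result will want to know what was seen in early and in established disease, and no such table is planned.

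**Working it through.** **Inputs from the documents.** Arms and size: "anticipated sizing of 25 individuals into 4 arms", so k = 4 and N = 100 (section 4.1.5 plans "an estimated 120 enrolled to achieve this number"). Unadjusted detectable effect: "This provides an effect level of 0.3370 using 80% power, with 0.05 significance established for curvature assessment". Adjusted detectable effect: "to 0.302 (assuming R^2 value of 0.2 for curvature direction, curvature degree, and baseline penile length".

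**Formula.** Power of the overall F test comes from the noncentral F distribution with df1 = k − 1 = 3, df2 = N − k − c, where c is the covariate degrees of freedom, and noncentrality λ = N f² / (1 − R²). Solve for the f that gives 80% power at alpha 0.05.

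**The plan's own figures.**

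- ANOVA (c = 0, R² = 0): df2 = 96, f = 0.3370. At that f, λ = 100 × 0.3370² = 11.36 and power is 0.800. This matches.
- ANCOVA (R² = 0.20): f is about 0.3370 × √0.80 = 0.3014 before counting covariate degrees of freedom. With c = 4 (direction 2, degree 1, length 1), df2 = 92 and f = 0.3017. This matches 0.302.

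Both figures are smallest detectable effects, so adjustment lowers the value from 0.337 to 0.302. The plan words this as an increase, which does not affect the point here.

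**Adding duration as one linear term** (c = 5, df2 = 91). The documents give no R² for duration, so every row after the first is an assumption.

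| Total R² | Detectable f | Power at f = 0.302 |
|---|---|---|
| 0.20 (duration adds nothing) | 0.302 | 80.1% |
| 0.22 | 0.298 | 81.2% |
| 0.25 | 0.292 | 82.8% |
| 0.30 | 0.282 | 85.6% |
| 0.35 | 0.272 | 88.2% |

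If duration is useless, the lost degree of freedom moves f from 0.3017 to 0.3018. In residual variance, R² of 0.25 is worth a factor of 0.80/0.75 = 1.07 and R² of 0.30 a factor of 0.80/0.70 = 1.14. These correspond to roughly 7 or 14 extra men on 100.

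**Chance imbalance.** The documents give no phase mix, so assume that 20% to 50% of men are in the acute phase, and ignore the strata, which do not use phase. In a simulation with 25 men per arm, two given arms differ by at least 20 percentage points with probability about 11% (at 20% acute) to 20% (at 50% acute). The largest gap among the four arms reaches 20 points with probability about 38% to 58%.

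**Subgroup size.** On the same assumption, each arm holds about 25 × 0.20 = 5 to 25 × 0.50 = 12.5 acute men.

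**The case against.** The strongest reply is that the chosen covariates are defensible. They cover both stratification factors plus baseline length, curvature is a secondary endpoint in a trial whose primary objective is safety, and nothing in the documents shows that duration predicts curvature change once those covariates are in the model. Randomization already protects the comparison in expectation, and even R² of 0.25 lowers f by only about 3% (0.302 to 0.292). All of that stands, and it is why this is a low-priority point.

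A second reply also stands. If traction works differently by phase, phase is an effect modifier, and a main-effect covariate does not address that. The covariate serves precision and chance imbalance only. A look at differing effects needs results by phase, and with perhaps 5 to 12 acute men per arm these can only be descriptive.

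Third, the questionnaire is not shown, so whether it records duration is unknown, and duration and phase are not the same variable. The phase table needs its own definition.

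Some stronger readings are tempting but not supported:

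- A reader might infer that the background makes phase the factor dividing positive from null curvature results. It does not. The null curvature findings in section 3 come from traction combined with intralesional injections and are not attributed to chronic disease.
- A reader might take section 3.3 as evidence that traction fails in chronic disease. Its stated reason is a lack of prior research.
- For the same reasons, the protocol cannot be said to treat phase as decisive for curvature.

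**Conclusion.** The point holds as a cheap improvement. On the protocol's own account the supporting curvature evidence comes from early disease, entry is open to all phases, and no stratum, covariate or named analysis uses phase or duration. The consequence is not bias. It is possible lost precision, unadjusted chance imbalance, and the absence of a planned description of curvature by phase.

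The benefit ranges from nothing (f stays at 0.302) to a modest gain (0.292 or 0.282 at assumed total R² of 0.25 or 0.30). The imbalance probabilities rest on an assumed acute share of 20% to 50%. The stated power figures are reproduced and are not in dispute.

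A reader might also infer that the trial will be unable to say to which phase its result applies. That goes too far: if the disease-history form records duration, the phase mix can be reported without any change to the model. What is missing is a prespecified plan to use it.

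**What to change.** In section 4.3.3:

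1. Add disease duration at baseline to the ANCOVA covariates, stating its functional form (for example, one linear term). Take it from the disease-history questionnaire in section 4.2.1, or add one question if it is not recorded there.
2. Report the 3-month curvature change by arm and by baseline phase, with the definition of phase fixed before analysis and the table labelled descriptive, without subgroup claims.

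The cost is one residual degree of freedom (92 to 91), possibly one form question, and subgroup figures that will be small and imprecise. Strata, sample size and visit schedule do not change.
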